5. STUDY SUBJECTS

5.1. Disposition of Subjects

The disposition of all enrolled subjects will be summarized in tables and presented in listings using the screening sample. A consort diagram will also be constructed to serve as a visual depiction of the flow of subjects through the study.

The numbers and percentages of subjects randomized (and in each analysis sample) will be displayed by randomized treatment group and overall. Reasons for early termination from the study and visit completion statistics will be presented. The reasons for discontinuing study treatment early will also be presented for any subjects who prematurely discontinue study treatment.

5.2. Demographic and Other Baseline Characteristics

Summary descriptive statistics, with no formal group comparisons, for baseline and demographic characteristics will be reported for the ITT sample by treatment group and overall. Additionally, these characteristics will be described for subjects who were screened but were not eligible for treatment. Characteristics to be summarized include age, race, ethnicity, sex, cause of death, and chest trauma for donors, and age, race, ethnicity, sex, pre-operative diagnoses, and medical histories for recipients. Additional relevant characteristics may be included.

6. STUDY OPERATIONS

6.1. Protocol Deviations

Protocol deviations will be listed by site with information such as severity of the deviation (major or non-major), type of deviation, date of occurrence, and the reason for the deviation. Protocol deviations may also be summarized in tabular format by severity and type of deviation.

6.2. Treatment Adherence

Treatment Groups:

- **Rituximab Group** – induction therapy with anti-CD20 mAb (375 mg/m²) IV on day 0 and day 12 post-transplant plus standard of care immunosuppression (thymoglobulin induction, tacrolimus or equivalent, MMF or equivalent, and steroids).
- **Placebo Group** – induction therapy with placebo IV on day 0 and day 12 post-transplant plus standard of care immunosuppression (thymoglobulin induction, tacrolimus or equivalent, MMF or equivalent, and steroids).

Randomization to one of the two groups will occur once the subject has received the transplant and is deemed hemodynamically stable. The first infusion must be administered within 12 hours of returning to the ICU following transplant. The second infusion should be administered on day 12 (\pm 2 days) post-transplant.

Adherence will be summarized for the ITT sample. The status of each infusion will be classified as complete, partial, or not done and the duration (or extent) of exposure will be calculated by determining the number of days between first and second infusions (+1) for each subject in the

sample. These variables will then be summarized using appropriate statistics in a table and subject-level details will be presented in a listing.

7. ENDPOINT EVALUATION

7.1. Overview of Efficacy Analysis Methods

7.1.1. Multicenter Studies

Study subjects will be recruited from 7 study sites.

Following database lock, if potentially impactful site-to-site variation is noted, basic descriptive analyses of baseline demographics, medical history, and key study endpoints will be repeated for each site individually in order to allow qualitative exploration of site-to-site variability.

7.1.2. Assessment Time Windows

Allowable visit windows are detailed in Section 8 of the protocol.

Unscheduled visits may also occur throughout the study if a subject develops symptoms of a respiratory viral infection (RVI) or a bronchoscopy is performed for suspicion of rejection or infection.

Generally, all data will be included in analyses, regardless of time of assessment.

7.2. Primary Endpoint

The primary endpoint is a composite of the earliest time from transplant to any of the following events during the follow-up period:

- Chronic allograft dysfunction (defined as the occurrence of confirmed BOS grade 0-p or higher or a diagnosis of Obliterative Bronchiolitis (OB)),
- Listed for re-transplant,
- or Death.

7.2.1. Computation of the Primary Endpoint

First, each component will be derived separately as described below.

- **Chronic allograft dysfunction**

- BOS component – Subjects with at least one confirmed diagnosis of BOS grade 0-p or higher, as defined in Section 7.5.3 of the protocol, will be considered to have met the BOS component of chronic allograft dysfunction. Rho will programmatically monitor the PFT data and notify sites of suspected BOS. Confirmation (or rule out) of BOS will then be made by the site PI and documented in the BOS PFT Decline CRF.

Subjects who do not meet this component must have at least one set of post-transplant PFTs reported in order to be considered evaluable and, as such, classified as not meeting the endpoint.

The date/day of the first occurrence of confirmed BOS will be used for analyses.

- OB component – Subjects with at least one episode of OB reported will be considered to have met the OB component of chronic allograft dysfunction. OB will be identified either as a reason for hospitalization or as a specific histopathological finding noted on a biopsy.

Subjects who do not meet this component must have at least one post-transplant biopsy reported in order to be considered evaluable and, as such, classified as not meeting this component.

For patients unable to perform PFTs (and will therefore have an unknown status for the BOS component), chest imaging data will be reviewed by the study Principal Investigator and Protocol Chair for any subjects designated as not meeting the OB component. The purpose of this review will be to identify any imaging changes consistent with airway obstruction that were not identified in the transbronchial biopsy tissue. If this comprehensive review of the imaging data yields a diagnosis of OB, the subject's OB classification will be changed from No to Yes, and the date of the imaging exam will be used as the date of OB diagnosis.

The date/day of the first occurrence of OB will be used for analyses.

- Once the status of the two components above is known, the chronic allograft dysfunction status for each subject will be classified per the rule below.
 - Chronic allograft dysfunction= Yes if BOS= Yes or OB= Yes
 - For these subjects, if more than one component is met then the earliest date/day will be used for analysis. Otherwise, the date/day of the only component met will be used for analysis.
 - Chronic allograft dysfunction= No if BOS= No and OB= No
 - For subjects who do not meet either component, data will be censored at the last time point where a subject's status is known.
 - Chronic allograft dysfunction= Unknown and considered not evaluable if
 - BOS= No and OB= Unknown *or*
 - BOS= Unknown and OB= No *or*
 - BOS= Unknown and OB= Unknown
- **Listed for re-transplant** – Subjects with a reported date of listing for re-transplant will be considered to have met this component of the primary endpoint. The date/day of re-listing will be used for analysis.

Subjects otherwise reported as not having been re-listed will be classified as not meeting this component. Data will be censored at the last time point where a subject's status is known.

Any subject not meeting the criteria to be classified as Yes or No for re-listings will be considered not evaluable for this component and classified as Unknown.

- **Death** – Subjects with a reported date of death will be considered to have met this component of the primary endpoint. All other subjects will be classified as not meeting this component. The date/day of death will be used for analysis; otherwise, data will be censored at the last time point where a subject's status is known. Once the status of each of the above components is determined, the primary endpoint status for each subject will be classified per the rule below.
- Primary Endpoint= Yes if

Chronic allograft dysfunction= Yes or Listed for re-transplant= Yes or Death= Yes

- For these subjects, if more than one component is met then the earliest date/day will be used for analysis. Otherwise, the date/day of the only component met will be used for analysis.

- Primary Endpoint= No if
Chronic allograft dysfunction= No and Listed for re-transplant= No and Death= No
 - For subjects who do not meet any of the components, data will be censored at the last time point where a subject's status is known.

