7.5.3. Chronic Allograft Dysfunction

Chronic allograft dysfunction is defined as BOS, Grade 0p and above, or histologic evidence of obliterans bronchiolitis.^{103, 105} For participants old enough to perform spirometry, BOS will be diagnosed locally based on the 2001 ISHLT diagnostic criteria shown in Table 7. Local sites will rule out acute rejection, acute infection and airway stenosis or narrowing prior to diagnosing BOS. Spirometry will be supervised by a trained technologist at each site.

BOS Grade	Classification
0	FEV ₁ > 90% of baseline and FEF ₂₅₋₇₅ > 75% of baseline
0p	FEV ₁ 81 to 90% of baseline and/or FEF ₂₅₋₇₅ ≤ 75% of baseline
1	FEV ₁ > 66-80% of baseline
2	FEV ₁ > 51-65% of baseline
3	FEV ₁ > 50% or less of baseline

Table 7: Classification of BOS

For participants unable to perform a pulmonary function test, BOS will not be determined. Obliterative bronchiolitis (OB) will be used as the outcome in this population. OB will be identified by histology according to the ISHLT report.

Biopsy to evaluate for OB will also be obtained from participants with unexplained air trapping on high resolution expiratory CT images or ventilation perfusion scanning and participants with unexplained obstructive changes on infant PFTs.

Chronic allograft dysfunction will be evaluated and treated as described in **Table 8**.

BOS Grade 0p	
 1. Reassess for contribution of reflux and/or infection and treat as appropriate. 2. Perform bronchoscopy and transbronchial biopsy. 3. If no OB on transbronchial biopsy consider open lung biopsy if rapidly progressive and monitor study participant closely.
BOS progressing to Grade 1 despite above interactions	
 1. Reassess for ongoing contribution of reflux and/or infection and treat as appropriate. 2. Re-biopsy (transbronchial or open lung biopsy). 3. Pulse with steroids (Methylprednisolone 10 mg/kg/day x 3 days) and use cytolytic therapy (Thymoglobulin®) in patients with lymphocytic inflammation in active OB lesions.
Evidence of OB on biopsy	Pulse with steroids and use cytolytic therapy (Thymoglobulin®; dosing as above) in patients with lymphocytic inflammation in active OB lesions.

Table 8: Evaluation and Treatment for Chronic Allograft Dysfunction

Subjects will be re-evaluated every 3 months following the diagnosis of chronic allograft dysfunction. If BOS grade progresses the local PI may consider:

- Photopheresis

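### SAP 7.2.1 leaves event-free children who cannot do spirometry without a primary-endpoint status, against protocol 7.5.3; dropping them would overstate event rates

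*SAP*

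**What the plan says.** **Protocol 7.5.3 (Chronic Allograft Dysfunction).** "For participants unable to perform a pulmonary function test, BOS will not be determined". The next sentence supplies the substitute: "Obliterative bronchiolitis (OB) will be used as the outcome in this population".

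**SAP 7.2.1 (Computation of the Primary Endpoint).**

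- The BOS component can be No only if at least one set of post-transplant PFTs was reported. Children who cannot do PFTs are acknowledged: "For patients unable to perform PFTs (and will therefore have an unknown status for the BOS component").
- If their OB is negative, two study leads review the chest imaging. That review can only turn OB from No to Yes.
- The CAD rule lists, under "Chronic allograft dysfunction= Unknown and considered not evaluable if", the combination "BOS= Unknown and OB= No".
- The composite is Yes if any component is Yes. It is No only under "Chronic allograft dysfunction= No and Listed for re-transplant= No and Death= No". No rule covers a composite with an unknown component.
- Nested under composite No is the censoring instruction: "For subjects who do not meet any of the components, data will be censored at the last time point" of known status.
- Re-listing has its own unknown category: such subjects "will be considered not evaluable for this component and classified as Unknown".

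**Elsewhere in the SAP.** Section 4 uses the ITT sample (all randomized subjects with at least a partial first infusion) for the primary endpoint, with no evaluability condition. Section 7.2.2 right-censors at the end of follow-up or at loss. Section 7.3.1 reuses the primary-endpoint definition for secondary CAD incidence.

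**The concern.** The protocol plans not to determine BOS in these children and names OB as their outcome. The SAP turns that planned non-determination into missing data. A child who is alive, not re-listed, biopsy-negative and negative on the extra imaging review still has unknown CAD, and so fits neither composite rule. The same child with OB, re-listing or death is a Yes. Read literally, having a status depends on having had an event.

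The example code in SAP 7.2.2 uses only status values 0 to 3, with nothing for unknown. A programmer must either set the status to missing, which removes the child from the Cox and Kaplan-Meier analyses, or set it to 0, which censors the child. The text supports either choice. The first removes only event-free subjects.

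The group is foreseeable. The age criterion is 21 years or younger with no lower limit, and Appendix 1 of the protocol lists PFTs with age restrictions and only where they are standard of care. Unknown OB with negative BOS, and unknown re-listing, fall into the same gap.

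**Working it through.** **1. Case by case, for a child with no post-transplant PFTs**

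| OB after biopsy and imaging | Death or re-listing | CAD, protocol 7.5.3 | CAD, SAP 7.2.1 | Composite, SAP 7.2.1 |
|---|---|---|---|---|
| Yes | any | Yes | Yes | Yes |
| No | yes | No | Unknown | Yes |
| No | no | No | Unknown | no rule applies |

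**2. Inputs**

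- Protocol 13.6: control rates of 74% at one year and 53% at two years. They fall with time, so they are read as event-free; planning HR 0.40.
- Protocol 3.1 and synopsis: 25 + 25 subjects, followed 1 to 4.5 years (censoring taken as uniform over that range).
- The share f unable to do PFTs is not in the documents; 10 to 40% is assumed.

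**3. Reproducing the planned control curve**

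S(t) = exp(−λt^k), with λ = −ln 0.74 = 0.301 and k = ln(ln 0.53 / ln 0.74) / ln 2 = 1.076. This returns 26% with events at one year and 47% at two years.

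**4. Direction, by algebra**

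If a fraction f is removed whenever event-free, an event proportion p becomes p / (1 − f(1 − p)), which exceeds p for any f > 0 and p < 1.

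- Control at 2 years, f = 20%: 0.47 / (1 − 0.2 × 0.53) = 0.47 / 0.894 = 52.6%. For f = 10, 30 and 40%: 49.6, 55.9 and 59.6%.
- HR 0.40 arm at 2 years: p = 1 − 0.53^0.40 = 22.4%; for f = 10, 20 and 30%: 24.3, 26.6 and 29.2%.

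**5. Simulation with the planned follow-up** (25 + 25, true HR 0.40, equal hazards in the two kinds of children, 4,000 trials per row; each cell is censored → dropped)

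| f | Children lost of 50 | Control event proportion | Control 2-year KM event estimate | Median HR | Shift in SE of log HR |
|---|---|---|---|---|---|
| 10% | 2.9 | 57 → 59% | 47 → 49% | 0.400 → 0.408 | 0.04 |
| 20% | 5.6 | 57 → 62% | 47 → 51% | 0.390 → 0.410 | 0.10 |
| 30% | 8.6 | 57 → 65% | 47 → 53% | 0.394 → 0.424 | 0.15 |
| 40% | 11.4 | 57 → 69% | 47 → 56% | 0.394 → 0.439 | 0.23 |

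The mean SE of log HR is 0.48; for example, ln(0.439/0.394) / 0.48 = 0.23. The chance that the upper 90% limit falls below 1 goes from 0.63–0.66 to 0.62, 0.62, 0.58 and 0.55.

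**6. Lower hazard in PFT-unable children**

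Protocol 2.1 gives 4-year BOS of 31% in infants against 54% at age 12 and over. With half the hazard, the control event proportion moves from 55 to 58%, 52 to 60%, 50 to 62% and 48 to 65% for f = 10 to 40%. The HR moves by at most 0.02.

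**7. No treatment effect**

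At true HR 1 (6,000 trials in each of eight settings), the chance of an upper 90% limit below 1 is 0.043–0.054 if dropped and 0.045–0.053 if censored. There is no inflation on average, although a chance imbalance between arms can move a single trial's HR either way.

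**8. Secondary CAD incidence, control arm, f = 20%, evaluable subjects only**

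If CAD carries 50, 70 or 90% of the event hazard (assumed), incidence moves from 28 to 33%, 40 to 45% and 51 to 57%.

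**9. Children with neither PFT nor biopsy**

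If they are 2, 5 or 10% and none of their CAD is seen, keeping them to the last visit gives a 2-year estimate of 46.3–46.7, 44.9–46.1 or 42.9–45.2%, against a full-detection value of about 47%. Dropping them unless they die or are re-listed gives 47.0–47.3, 47.1–47.6 or 47.2–48.2%. Neither rule is neutral for this subgroup.

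**The case against.** **Dropping is never stated.** The ITT definition, the right-censoring in SAP 7.2.2 and the Death rule (anyone without a death date is censored at last known status) all point to keeping these children. The bullet on subjects who meet none of the components can be read the same way. This stands as far as it goes: if they are censored, the effect in the tables disappears. But that bullet sits under composite No, which these children cannot satisfy, and the explicit not-evaluable label points the other way.

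**Secondary endpoints default to ITT.** SAP 7.3 says so. It does not say how a not-evaluable CAD status enters the proportion, so the denominator remains open.

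**Censoring is not free of error either.** Without spirometry, some CAD will be missed. With 20% unable, half of their CAD detected, and CAD carrying 70 to 90% of the hazard (all assumed), the control 2-year estimate of 47% becomes about 43–44% if they are kept and 49–50% if dropped. So the claim of no bias under censoring holds against the protocol's own OB outcome, not against CAD as defined for children with spirometry. That is a real limitation, but the protocol accepted it by naming OB as the outcome.

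**The effect on the main estimate is small, and the share is assumed.** Both are true. The larger shifts need the upper end of the range, and a child who ever provides one set of post-transplant PFTs is no longer affected on the BOS side.

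**Conclusion.** The concern holds. The CAD rule in SAP 7.2.1 contradicts protocol 7.5.3, and the composite rules give no status to an event-free child who cannot do PFTs. This is a stated rule that departs from the protocol, not merely absent detail.

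The numerical harm is conditional on the children being dropped. It then falls mainly on absolute rates: the composite event proportion, the Kaplan-Meier event-free estimates in SAP 7.2.3 and possibly secondary CAD incidence. At an assumed 20% share, that is about 4 to 5 percentage points for the control composite under equal hazards. A real benefit is pulled slightly towards HR 1. The sizes rest on the assumed share, on reading 74% and 53% as event-free, on uniform follow-up of 1 to 4.5 years and, for CAD incidence, on the assumed CAD share of the hazard. The direction, if they are dropped, does not depend on these values. It should be fixed before unblinding.

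**What to change.** Amend SAP 7.2.1:

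1. For participants unable to perform PFTs, determine CAD from OB alone (biopsy plus the planned imaging review), so that OB No gives CAD No, as in protocol 7.5.3. Use the same definition for secondary CAD incidence and state its denominator.
2. State that event-free ITT subjects stay in the composite Cox and Kaplan-Meier analyses, right-censored under one rule common to all subjects and both arms: the last date on which event status was assessed. Appendix 1 of the protocol schedules an assessment of CAD, death and re-listing at study visits, so the last visit with that assessment completed is a usable date.
3. Write an explicit censoring rule for OB unknown (no post-transplant biopsy, with or without PFTs) and for re-listing unknown. Do not count a bare contact as a CAD assessment. Test the rule in a sensitivity analysis, for example by censoring at the last PFT, biopsy or reviewed imaging.
4. Keep the complete-status rule only as a sensitivity analysis, and tabulate CAD ascertainment (PFT, biopsy, imaging) by arm.

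**Cost:** SAP wording, a few lines of derivation code, one sensitivity run and one table; no new data. **Downside:** CAD is less completely ascertained without spirometry. Routine biopsies end at month 18 (protocol 8.4), so later OB in these children depends on symptomatic biopsies and standard-of-care imaging. The ascertainment table lets readers judge this.

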7.2.2. Primary Analysis of the Primary Endpoint

As the data allow, a Cox proportional hazards model will be used to compare treatment groups on the time to endpoint, allowing for right-censoring at the end of the follow-up period or at time of loss to follow-up. Estimates of the hazard ratios (HR) and their two-sided 90% confidence intervals will be produced. HR estimates <1 will indicate rituximab efficacy. For example, if an HR<0.85 is considered as indicating clear efficacy, then an HR estimate and 90% confidence interval of 0.33 (0.16, 0.68) will provide excellent support for clear efficacy; whereas an HR= 0.55 (0.28, 1.07) would provide fair to good support for efficacy, even though it would fail to reach significance for the usual test of HR= 1.

The model will be run on both the ITT and PP samples, as events allow.

Model diagnostics will include an evaluation of the proportional hazards assumption and of each observation for influence on model parameters. The proportional hazards assumption will be assessed by testing for a significant interaction between treatment group and the time-to-event variable.

An example of SAS code to be used for the primary model:

```
Proc phreg;  
  class treatment_group(ref='Placebo');  
  model event_day * endpoint_status(0) = treatment_group intterm /  
risklimits ties=efron alpha=0.1;  
  intterm= treatment_group_01 * event_day;  
run;
```

Note: *intterm* represents the interaction term that can be used to test the proportional hazards assumption and *treatment_group_01* represents *treatment_group* coded as a 0, 1 variable where 0=placebo and 1=rituximab. This term will be used for testing the assumption only and will not be included in the final model.

To estimate the hazard function of each of the components, separately, the following models will be used.

An example of SAS code to be used for the analysis of competing risks:

*This is the model for Death;

```
Proc phreg;  
  class treatment_group(ref='Placebo');  
  model event_day * endpoint_status(0,1,2) = treatment_group /  
risklimits ties=efron alpha=0.1;  
run;
```

*This is the model for Listed for Re-transplant;

```
Proc phreg;  
  class treatment_group(ref='Placebo');  
  model event_day * endpoint_status(0,1,3) = treatment_group /  
risklimits ties=efron alpha=0.1;  
run;
```

*This is the model for Chronic Allograft Dysfunction;

```
Proc phreg;  
  class treatment_group(ref='Placebo');  
  model event_day * endpoint_status(0,2,3) = treatment_group /  
risklimits ties=efron alpha=0.1;  
run;
```

7.2.3. Sensitivity Analyses of the Primary Endpoint

Given the likelihood of little to no events for one or more of the 3 components of the primary endpoint, a reduced competing risks model will be used excluding any component not observed. Additionally, a time-to-first-event model utilizing the Kaplan-Meier framework will be employed to produce estimates of the event-free rate of the composite endpoint and its individual components.

Furthermore, demographic and other clinical covariates (e.g., the presence or absence of pre-transplant auto or allo-immunity) may be included in these secondary analyses. The decision of what to include may be based on clinical experience, literature review, or exploratory data analysis done following database lock but prior to unblinding the treatment assignments.

An example of SAS code to be used:

```
Proc lifetest plots=(survival(atrisk));  
  time event_day * endpoint_status(0);  
  strata treatment_group;  
run;
```

